**Aim 2: To assess the substitutability of menthol cigarette alternatives.** [*H2a: A significantly higher portion of product preference selections for Phase 2 will favor nmC than all other alternatives. H2b: Participants' use of study products will significantly increase over the one-week substitution period. H2c: Under simulated UBMC ban conditions, >80% of participants will substitute at least 50% of their UBMC use with study product.]*

**Aim 3: To evaluate which product characteristics and perceived effects influence greater substitution.** *H3: Participants reporting higher product satisfaction, including "throat hit", menthol-specific sensory effects,*

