### Recruitment Feasibility and Retention

**Recruitment:** We intend to recruit 135 current menthol cigarette smokers (and assume 20% attrition) over a 16-month period (4 months of study preparation, 16 months of recruitment, and 4 months of data cleaning/analysis and manuscript prep). Therefore, we need ~6 participants to be recruited and complete study procedures each month to achieve our goal; we are confident that our recruitment approaches will yield sufficient numbers given our successful history of recruitment for other tobacco-related research of similar design. Menthol cigarette smokers will be recruited from advertisements through a variety of media outlets and the internet, including Study Search, as well as community events. Participants from other studies who have agreed to be contacted regarding other study opportunities will also be contacted. Staff from those studies will prepare contact letters/emails and call participants on behalf of this study. Participants interested will be referred to this study for screening. Participants will access the screening questionnaire using a public survey link generated by REDCap. Based on our team's previous studies we conservatively assume a 20% attrition rate; thus, we will need to recruit 135 participants to have 80 complete the study. Menthol smokers will be screened over the telephone. Participants who meet the following eligibility criteria will be asked to take part in the study.

**Inclusion Criteria:** 1) a current menthol cigarette smoker (>90% menthol cigarette use;  $\geq 5$  cigarettes per day) for at least the past 6 months, 2) between 21-24 (young adult or 25-50 years old (aged 25+), 3) willing to provide informed consent and abstain from all tobacco and nicotine use for at least 12 hours prior to the five lab sessions, 4) willing to complete two weeks of daily dairies, 5) read and speak English, and 6) have access to a smart phone or email

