## Addiction and Behavior Related to Menthol Cigarette Substitutes

approximately 2 hours each. During this period, participants will complete one week of daily diaries to assess their usage of UBMC.

Preferred Study Product *Ad libitum*-Observational Use Period (Phase 2): During the preferred study product observational use period, participants will be provided products at no cost. Study products will be provided in a 1.2 to 1 ratio based on self-reported use at the time of screening. This slight over appropriation helps to ensure that participants have enough study product available so to not artificially limit use, while also not oversupplying and potentially artificially increasing use beyond what would be usual. Participants will be instructed to completely switch and exclusively use the study product during the 1-week time period. During this period, participants will complete one week of daily diaries. If the participant has not responded after 3 prompts, the assessment will be recorded as missed.

Final Lab Session – Simulated Menthol Cigarette Ban Using a Progressive Ratio Task (Phase 3): Following the one-week use period, participants will come to the lab following 12-hr nicotine abstinence confirmed by eCO. To simulate the effect that restricting menthol in cigarettes would have on increasing (or not) preference for other alternative menthol substitutes, participants will complete a 90-minute concurrent choice task with differential cost (effort) required to earn 2 puffs from their UBMC (10 clicks increasing to 7200 ) versus their preferred study product (always 10 clicks) from Phase 2. This session will last approximately 3 hours.

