
**Addiction and Behavior Related to Menthol Cigarette Substitutes**

-0.2 indicates complementarity, and CPE between -0.2 and 0.2 indicate independence of the two products. Consistent with previous studies conducted by [name], the PR task will simulate the effect that restricting menthol in cigarettes would have on increasing (or not) preference for other alternative menthol substitutes. Participants will complete a 90-minute concurrent choice task with differential cost (effort) required to earn the reinforcement (2 puffs) from their UBMC and the study product (mFLC,mRYO or nmC). Puffs from the study product can be earned by clicking a computer mouse 10 times on a picture of the study product, but to earn two puffs of the UBMC, they will be required to make escalating response requirements (computer mouse clicks) according to the following schedule: 10, 160, 320, 640, 1280, 2400, 3600, 4800, 6000, 7200. A maximum of 10 reinforcers (20 puffs) per session will be allowed. The proportion of reinforcers earned is considered to provide an index of the strength of the reinforcing effects of the product. Participants will be informed of the differential sequence between products and instructed that the sessions are 3 hours in length no matter how much or how little they respond. Daily diaries will assess UBMC/study product smoked per day, product satisfaction and pleasure (see Table 1 for specific daily diary measures). [Substitution assessed via use behavior during Phase 2 will be operationalized as the ratio of study product to UBMC used, with a ratio > 0 indicating any substitution and a ratio > 1 indicating substitution of study product for the UBMC at least 50% of the time.]

Table 1. Measures

Measures	Phase 1:			Phase 2:	Phase 3:
	3 in-lab visits			1-week	Final Lab
	Visit 1	Visit 2	Visit 3	Visit 4	Visit 5
Background Measures					
Exhaled CO Abstinence verification	X	X	X	X	X
Pregnancy Test	X	X	X	X	X
Exhaled carbon monoxide	X	X	X	X	X
Breath Alcohol Concentration (BrAC)	X	X	X	X	X
Taste testing strips (PROP)	X				
Sociodemographic measures	X				
Cigarettes Use/Tobacco Use Hx (EDSHC)	X				
Menthol Subscales	X				
Readiness Rulers	X				
Product Use Status	X				
Product Use Detailed Assessment	X				

Addiction and Behavior Related to Menthol Cigarette Substitutes

Fagerstrom	X				
Abuse liability					
Smoking topography	X	X	X	X	
Drug Effects/Liking Questionnaire	X	X	X	X	X

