## E. Statistical Methods

### 1. Power Analysis

Since our main goal is to evaluate the substitutability of menthol alternatives in the context of a menthol cigarette ban, statistical power is based on differences in abuse liability measures (Hypothesis 1a) and product substitution (Hypothesis 2c). Sample size estimates relied on means and standard deviations of data collected as part of a University of Vermont laboratory study examining the abuse liability of cigarettes containing different doses of nicotine. A sample size of 80 subjects has 81% power to detect decreases in product satisfaction of up to 50% compared to their usual brand (mean for UBMC 5.5, SD 1.3). In addition, a sample size of 80 participants has greater than 80% power to detect decreases of 68%–72% in the cigarette purchase task indices of maximum expenditure, maximum price and price sensitivity, similar to what we found in our laboratory study. This sample size also provides 81% power to estimate 80% use of the preferred alternate product more than half the time during Phase 2 with a 95% confidence interval of 66%–94%.

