### 2. Data Analytic Plan

Statistical analyses will be performed using SAS 9.4 and an alpha of .05. Background measures will be summarized by product (UBMC, mFLC, mRYO, nmC), as appropriate. Continuous variables will be presented as mean  $\pm$  SD; categorical variables will be presented as counts and proportions. We will apply a transformation to normalize the distribution and stabilize the variance of the residuals where appropriate.

Hypotheses 1a and 1c: We will use Repeated Measures Analysis of Variance with Tukey-adjustment to examine differences between the alternatives and the UBMC in abuse liability assessed at each product lab session. Assuming statistically significant product differences, this post-hoc test will allow us to not only compare each product to the UBMC, but will also allow comparison of the alternative products with each other. Because product introduction in Phase 1 will be randomized using a Latin Square, a fixed effect for session and a random effect for sequence will be included in all analyses.

Hypothesis 2a: Product preference will be examined using a Chi-Square Test, comparing the proportions of participants choosing each alternate product for further use.

Hypothesis 2b: We will examine the trajectory of use behavior outcomes using Linear Mixed Model (LMM) regression analysis. We will employ a random intercept or slope parameter, as appropriate, and model the covariance structure for the repeated outcome measures, while accounting for potential confounders, including gender and baseline cigarettes/day.

Hypothesis 2c: This aim will be analyzed as a Chi-Square Test of Goodness of Fit to test the proportion of use compared to 80%.

Hypothesis 3: We will examine whether differences in product characteristics and changes in perceived effects collected via daily diary are associated with increased substitution of the alternate product over the seven-day period using generalized LMM regression analysis, similar to that outlined in H2b.

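### Power Analysis (E.1), 80 participants: the H2c interval should be about 71%–89%, the H2c 81% is not power for a share above 80%, and satisfaction power exceeds 99.9%

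*Combined protocol and SAP*

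**What the plan says.** Section E.1 bases power on H1a and H2c and uses 80 participants throughout.

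- **Satisfaction.** "A sample size of 80 subjects has 81% power to detect decreases in product satisfaction of up to 50% compared to their usual brand". The usual-brand mean is given as 5.5 with SD 1.3. No SD of the within-person difference and no correlation is given.
- **H2c.** The same sample size is said to provide "81% power to estimate 80% use of the preferred alternate product more than half the time during Phase 2". The end of that sentence attaches the interval to this use: "more than half the time during Phase 2 with a 95% confidence interval of 66%–94" per cent.

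The hypothesis itself (section A, Aim 2) reads: "Under simulated UBMC ban conditions, >80% of participants will substitute at least 50% of their UBMC use with study product". Section E.2 gives the test: "This aim will be analyzed as a Chi-Square Test of Goodness of Fit to test the proportion of use compared to 80" per cent, at alpha .05.

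The Detailed Study Procedures identify the simulated ban with the last visit: "Final Lab Session – Simulated Menthol Cigarette Ban Using a Progressive Ratio Task (Phase 3"). Section D.3 (Measures) defines the 50% threshold only for the Phase 2 diaries: "a ratio > 1 indicating substitution of study product for the UBMC at least 50% of the time".

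On numbers, Recruitment Feasibility and Retention says the investigators "conservatively assume a 20% attrition rate; thus, we will need to recruit 135 participants to have 80 complete the study". The Abstract gives 100 participants.

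**The concern.** The proportion, the confidence level and the sample size behind 66%–94% are all printed in E.1, and they do not produce that interval. The 81% attached to it is described as power to estimate 80%. But 80% is the null value of the planned test, so an observed 80% would give H2c no support. A halving of satisfaction is more than two SDs, an effect for which 80 within-person comparisons cannot have power as low as 81%.

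The H2c figure matters most. A reader will take it that the study has 81% power for a hypothesis that drives its size. If H2c is true by a moderate margin, the test will often fail to show it, and a non-significant result could be read as weak substitution in work meant to inform a regulatory decision. The satisfaction error alone needs only clarification, but it hides how small a difference the study can detect.

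**Working it through.** **Inputs.** From E.1: n = 80; share 0.80; usual-brand satisfaction mean 5.5, SD 1.3; fall of 50%. From E.2: chi-square goodness of fit against 0.80, alpha .05 (taken as two-sided, since sidedness is not stated), and Tukey adjustment over four products. Assumed: within-person correlation ρ between 0 and 0.5, and SD 1.3 on every product.

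**1. The interval.**
- Wald: 0.80 ± 1.96 × √(0.8 × 0.2 / 80) = 0.80 ± 0.088, so 71.2%–88.8%.
- Wilson: 70.0%–87.3%. Exact: 69.6%–88.1%. A 99% Wald interval is still narrower than the printed one, at 68.5%–91.5%.
- Sample size for a half-width of 14 points: 1.96² × 0.16 / 0.14² = 31.4.

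No standard method tried gives 66%–94% at n = 80.

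**2. The H2c power.** Under the null the expected count is 64, with SD √(80 × 0.8 × 0.2) = 3.58. A count of 71 gives z = 7/3.58 = 1.957, just short of 1.96; 72 gives 2.24. The test therefore rejects at 72 or more (supporting H2c) or at 56 or fewer (against it). Exact binomial probability of 72 or more, with the same calculation for 108 completers (rejection from 95 upward):

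| True share | n = 80 | n = 108 |
|---|---|---|
| 85% | 13% | 24% |
| 90% | 59% | 81% |
| 92% | 81% | 95% |
| 94% | 95% | >99% |

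The 108 is 135 × 0.8, the number left after the stated attrition. At 108 the Wald interval is 0.80 ± 0.075, or 72%–88%.

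*Can the printed 81% be reproduced?* Yes, as a contrast between 80% and 66%. If the true share is 66%, the probability of 56 or fewer is 0.808, and the arcsine formula gives 0.811. So 66%–94% may be a detectable range labelled as a confidence interval. That is an inference; the arcsine formula is symmetric in the two shares, so the direction cannot be settled. At 94%, the other end of the band, power is 95%, not 81%.

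**3. Satisfaction.** The fall is 0.5 × 5.5 = 2.75 points, and 2.75 / 1.3 = 2.1 SD. The SD of the paired difference is 1.3 × √(2(1 − ρ)): 1.3 at ρ = 0.5, 1.84 at ρ = 0, and at most 2.6 (ρ = −1). The noncentrality 2.75 × √80 / SD of difference is 18.9, 13.4 and 9.5 respectively. Power exceeds 99.9% in each case, with or without the Tukey adjustment.

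For 81% power the standardised difference is 0.321 unadjusted, so 2.75 points would need an SD of the difference of 2.75 / 0.321 = 8.6. Turned round, the fall detectable with 81% power is:
- unadjusted: 0.321 × 1.3 = 0.42 to 0.321 × 1.84 = 0.59 points (8%–11% of 5.5);
- Tukey (q = 3.66; standardised difference 0.388): 0.50 to 0.71 points (9%–13%).

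**4. The phase.** E.1 counts use in Phase 2. H2c speaks of the simulated ban, which the Specific Aims and the Detailed Study Procedures both assign to Phase 3. The only definition of the 50% threshold is the Phase 2 diary ratio. The powered outcome and the hypothesised outcome are therefore not the same.

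**The case against.** The best defence concerns H2c. E.1 speaks of power to estimate 80%, and never says in words that it has 81% power to show more than 80%. On that view the fault is an unstated alternative rather than wrong arithmetic, and the true shares in the table are the review's, not the plan's. It is correct that the shares are illustrative and that the origin of the figure cannot be established. There is even a further candidate: a continuity-corrected Wald interval with n = 40 is 66.4%–93.6%, and 40 would be half of 80, one age stratum if the completers split evenly. None of this rescues the sentence. E.1 ties the figure to 80 participants and names H2c as a basis for power; a detectable range is not a confidence interval; and power to detect a shortfall to 66% is power to contradict H2c.

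The power values are also sensitive to the discreteness of the test. With 81 completers they become 21%, 71%, 89% and 98%. At n = 80 and a true share of 90%, a one-sided exact test has 72%, and a one-sided z-test about 83% with actual size 0.056. This stands as a caution about precision. It does not turn an unqualified 81% into the power of the planned test.

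On numbers, the Abstract's 100 less 20% is exactly 80, which suggests that 80 is the intended figure and 135 a later one. That makes the 108 scenario less certain, but the plan still has to say which number holds.

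On satisfaction, only the usual-brand SD is given, and the wording about decreases up to 50% is loose. Yet for 81% at 2.75 points the alternative's SD would have to be at least 8.6 − 1.3 = 7.3 on a measure with mean 5.5. If a smaller fall was meant, E.1 does not name it.

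**Conclusion.** The concern holds. At n = 80 the H2c interval is about 71%–89%, a half-width of 8.8 points rather than 14. The printed 81% is not power for H2c: in the supporting direction the planned two-sided test reaches 81% only at a true share of about 92%, and has 13% and 59% at 85% and 90%. Satisfaction power for a 50% fall is above 99.9% for any correlation, given SD 1.3 on both products. The phase of the H2c outcome is contradictory.

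The interval and satisfaction errors understate what the study can do; the H2c statement can mislead in the other direction, and it is the reason the passage must be corrected. The detectable satisfaction falls depend on the assumed correlation of 0 to 0.5. The purchase-task power (decreases of 68%–72%) cannot be checked from the documents and is not challenged.

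**What to change.** 1. Replace the H2c sentence in E.1 with: *With 80 completers, an observed 80% has a 95% confidence interval of 71%–89%. Under the planned chi-square goodness-of-fit test against 80% (two-sided, alpha .05), power to show that more than 80% of participants substitute is 13%, 59%, 81% and 95% if the true share is 85%, 90%, 92% and 94%.* If the 66%–94% band is to stay in some form, state the sample size and method behind it and do not call it a confidence interval.
2. Restate satisfaction as 81% power for a fall of at least about 0.4–0.6 points unadjusted, or 0.5–0.7 points with the Tukey adjustment, and state the within-person correlation assumed.
3. Name one phase for the H2c outcome and use it in the Aims, E.1 and E.2, with the 50% threshold defined for that phase.
4. Reconcile 80 completers with 135 recruits and 20% attrition (108) and with the Abstract's 100. Recompute item 1 if the number is not 80, since the test's power shifts noticeably even between 80 and 81.

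The cost is wording. The planned test, alpha and recruitment target are unchanged. The stated H2c power becomes less favourable and the satisfaction power more so.

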### 2. Data Analytic Plan

Statistical analyses will be performed using SAS 9.4 and an alpha of .05. Background measures will be summarized by product (UBMC, mFLC, mRYO, nmC), as appropriate. Continuous variables will be presented as mean  $\pm$  SD; categorical variables will be presented as counts and proportions. We will apply a transformation to normalize the distribution and stabilize the variance of the residuals where appropriate.

Hypotheses 1a and 1c: We will use Repeated Measures Analysis of Variance with Tukey-adjustment to examine differences between the alternatives and the UBMC in abuse liability assessed at each product lab session. Assuming statistically significant product differences, this post-hoc test will allow us to not only compare each product to the UBMC, but will also allow comparison of the alternative products with each other. Because product introduction in Phase 1 will be randomized using a Latin Square, a fixed effect for session and a random effect for sequence will be included in all analyses.

Hypothesis 2a: Product preference will be examined using a Chi-Square Test, comparing the proportions of participants choosing each alternate product for further use.

Hypothesis 2b: We will examine the trajectory of use behavior outcomes using Linear Mixed Model (LMM) regression analysis. We will employ a random intercept or slope parameter, as appropriate, and model the covariance structure for the repeated outcome measures, while accounting for potential confounders, including gender and baseline cigarettes/day.

Hypothesis 2c: This aim will be analyzed as a Chi-Square Test of Goodness of Fit to test the proportion of use compared to 80%.

Hypothesis 3: We will examine whether differences in product characteristics and changes in perceived effects collected via daily diary are associated with increased substitution of the alternate product over the seven-day period using generalized LMM regression analysis, similar to that outlined in H2b.

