**The goal of the proposed study is to examine the abuse liability and substitutability of plausible menthol cigarette alternatives.** Using an in-laboratory and *ad libitum* outpatient mixed design, current menthol cigarette smokers (N=135) will complete a three phase, 3-week study: in Phase 1, utilizing a randomized crossover design, participants will complete [4 smoking sessions], smoking a different product each session to examine each product's abuse liability, demand, and topography. Products will include participants' usual brand menthol cigarette (UBMC) as well as 3 commercially-available alternatives, including mFLC, mRYO product, [*and non-mentholated cigarette (nmC).*] Participants will complete one-week of daily diaries after smoking session 1 in phase 1 to assess their usage of usual brand menthol cigarette (UBMC). In Phase 2, to assess uptake, changes in subjective effects, and use over time, participants will [*select their preferred study product from Phase 1*] and be instructed to completely substitute the product for their UBMC for one week. Participants will complete daily diaries during this period to more accurately assess substitution and perceived effects in real-time. In Phase 3, participants will complete a final in-lab visit to assess the substitutability of [*their preferred product from Phases 1 and 2,*] under simulated ban conditions using a progressive ratio task. In all phases, multiple domains of abuse liability will be assessed, including product administration (in-lab topography and daily diary self-report measures), product liking/craving and withdrawal suppression (in-lab and daily diary self-report).

**Aim 1: To assess the abuse liability of menthol cigarette alternatives.** *H1a: Alternatives will [have similar use topography and significantly reduce nicotine craving/withdrawal similar to UBMC, but (H1b) UBMC will show significantly greater demand indices and liking/satisfaction compared to alternatives. H1c: Among alternatives, nmC will show the greatest demand and liking/satisfaction, followed by mFLC, and lastly mRYO.]*

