## Addiction and Behavior Related to Menthol Cigarette Substitutes

### 3. Measures

Questionnaire data will be collected over the phone or in-person by a trained research assistant and data will be entered into a secured and encrypted database using REDCap. See Table 1 for timing of measures. Sociodemographic measures will assess participant age, sex, marital status, ethnicity, employment status, occupation, years of education, and socioeconomic status. Tobacco use history will assess years of smoking, age of smoking onset, average number of cigarettes per day, number and recency of previous 24-hour quit attempts, number of smokers in the household, prior use of nicotine replacement therapy and other stop smoking medications, and history of receiving smoking cessation counseling. It will also assess tobacco type, brand, frequency, quantity, and duration of use all of nicotine/tobacco products including cigars, cigarillos, little cigars, pipe tobacco, chewing tobacco, snuff, snus, EC/vape/mod/APV/e-hookah, combusted tobacco hookah, and dissolvable tobacco. Cigarette Dependence will be measured with the 12-item Cigarette Dependence Scale. Exhaled carbon monoxide will be assessed at the start of each study visit. Abuse liability of products will be measured across several domains 1) smoking puff topography, 2) subjective effects, 3) behavioral economic choice tasks, and 4) craving for and suppression of craving and withdrawal. Smoking puff topography will be measured with CReSS Pocket Topography Device by Borgwaldt. The device uses a pressure transducer integrated into a plastic cigarette holder to produce measures of puff count, puff duration, inter-puff-interval, puff flow rate, average puff volume, and total puff volume. Puff topography is a validated and sensitive behavioral measure of abuse liability, is highly stable and associated with level of dependence and predicts level of exposure to harmful tobacco-related toxicants. An adapted version of the Drug Effects/Liking Questionnaire will assess the desire and liking of UBMC and all three study products, positive and negative effects (i.e., side effects), and perceived strength and effectiveness. [The modified Cigarette Evaluation Questionnaire (mCEQ) will also assess subjective responses to cigarettes (e.g., reward, satisfaction).] The Cigarette Purchase Task will ask participants how much they would be willing to pay (ranging from 0¢ to \$1,120) to smoke each product. Given that the study products will look similar to cigarettes, we will retain the original language (e.g., “1 cigarette”) in the purchase task. [Willingness to spend more will indicate greater abuse liability.] Smoking urges/craving will be measured using the Tiffany-Drobes Questionnaire of Smoking Urges: Brief Form. This is a 10-item measure where participants rate smoking-related items (“All I want right now is a cigarette.”) on a 7-point Likert scale ranging from ‘strongly agree’ to ‘strongly disagree’. Similar to previous studies, we will collapse the items into two previously identified factors (Factor 1: strong desire and intention to smoke; Factor 2: anticipation of relief from withdrawal symptoms). Nicotine withdrawal will be assessed using the empirically validated 15-item version of the Minnesota Nicotine Withdrawal Scale. This measure assesses smoking craving, anger/irritability, anxiety, depressed mood, restlessness/difficulty concentrating, increased appetite, sleep problems, and somatic symptoms (nausea, constipation, sore throat, dizziness, coughing). [Subjective effects (daily diary) of the Phase 2 substitute product will be derived from daily diaries assessing product satisfaction and pleasure.] [Substitutability of products will be assessed using a Cross-Price Task, a Progressive Ratio (PR) Task and daily diaries. A Cross-Price Task in Phases 1 and 3 will estimate substitutability of the study product for the UBMC. Participants will be asked how many study products and UBMCs they would consume when the price of the study product is fixed at \$1 and the UBMC prices escalate. The data are then fit to an exponential equation that indicates whether the fixed-price product substitutes for the primary product, and the degree of substitution. Cross price elasticity (CPE) for each study product compared to UBMC  $> 0.2$  indicates substitution,  $CPE <$

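### As planned, the H2a chi-square does not test nmC against its rivals, and the H1a difference tests do not test similarity to UBMC

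*Combined protocol and SAP*

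**What the plan says.** **Hypotheses (A. Specific Aims).** H1a: the alternatives will "have similar use topography and significantly reduce nicotine craving/withdrawal similar to UBMC". H1b: "UBMC will show significantly greater demand indices and liking/satisfaction compared to alternatives". H2a: nmC will take a significantly larger share of the Phase 2 choices than all the other alternatives.

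**Analysis (E.2 Data Analytic Plan).** For Aim 1: "Hypotheses 1a and 1c: We will use Repeated Measures Analysis of Variance with Tukey-adjustment to examine differences between the alternatives and the UBMC". The follow-up contrasts are introduced by "Assuming statistically significant product differences, this post-hoc test will allow us to not only compare each product to the UBMC", and the same sentence adds comparisons among the alternatives. For H2a, E.2 names a chi-square test on the proportions choosing each alternative and nothing further. It has no entry for H1b. Alpha is 0.05. No equivalence margin or confidence-interval rule for similarity appears in the document.

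**Power (E.1 Power Analysis).** "statistical power is based on differences in abuse liability measures (Hypothesis 1a"), and then "A sample size of 80 subjects has 81% power to detect decreases in product satisfaction", followed by the purchase-task indices.

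**Sample size (Recruitment Feasibility and Retention).** "we conservatively assume a 20% attrition rate; thus, we will need to recruit 135 participants to have 80 complete the study".

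**Outcomes (3. Measures).** Topography gives "puff count, puff duration, inter-puff-interval, puff flow rate, average puff volume, and total puff volume". Craving is scored as two factors, and withdrawal is measured on one scale. Under Detailed Study Procedures, subjective measures are taken before smoking and at five times afterwards.

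**The concern.** Two hypotheses are paired with tests that answer a different question.

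- **H2a** claims that one named product leads. A chi-square across three products asks whether the shares are all equal. It can reject because one product is unpopular, and it takes no account of which product is on top.
- **H1a**, in part, claims similarity. A test of difference can reject similarity but cannot establish it. A non-significant result does not separate 'similar to UBMC' from 'too imprecise to tell'. On the natural reading, the contrasts with UBMC are examined only after a significant product effect, so in the case that matters most for H1a they might not be shown at all.

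The study means to inform regulatory estimates of how far these products would replace menthol cigarettes. Whether nmC is truly preferred, and whether the alternatives act like UBMC, are therefore central conclusions.

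**Working it through.** **The plan's own figure.** The 81% in E.1 is the only power figure for an Aim 1 subjective measure with its inputs stated. A 50% fall from 5.5 is 2.75. With SD 1.3 and, as the least favourable case tried, zero within-person correlation, the SD of the paired difference is 1.3×√2 = 1.84. Then 2.75/1.84×√80 ≈ 13.4, and power is about 100%, so 81% is not reproduced. That is a separate matter. It concerns a difference in satisfaction, which is an H1b outcome, and says nothing about similarity.

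**Sample size.** The stated inputs conflict: 135×0.8 = 108, not 80. Key results are given at both.

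**H2a, example.** Illustrative choices nmC/mFLC/mRYO = 37/35/8, n=80, expected 26.67 each.
- Chi-square = (10.33² + 8.33² + 18.67²)/26.67 = 19.675 on 2 df, p=0.00005. About 13.1 of the 19.7 comes from mRYO's shortfall.
- nmC against mFLC, exact binomial 37 of 72: p=0.91.
- Swapping the first two counts (35/37/8) leaves chi-square and p unchanged, although nmC is now second.
- At n=108, 50/47/11 gives p=0.000002 overall and 0.84 for nmC against mFLC.

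**H2a, operating characteristics** (1,000,000 multinomial draws; shares are assumed because the document gives none). The two-test rule is defined under the fix.

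| True shares | Chi-square significant with nmC top, n=80 / 108 | Two-test rule, n=80 / 108 |
|---|---|---|
| 45/45/10 | 48% / 48% | 2% / 2% |
| 50/30/20 | 85% / 94% | 46% / 60% |
| 60/25/15 | not tabulated | 92% / 98% |

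**H1a, chance of missing a real difference.** No SD is given for any H1a outcome, so differences are in SDs of the paired difference, under compound symmetry. The Tukey critical value is q(0.95; 4, df)/√2 = 2.587 at n=80 (df 237) and 2.583 at n=108 (df 321). P(missed) = Φ(critical value − d√n).
- d=0.2, n=80: Φ(2.587 − 1.789) = 79%; n=108: 69%.
- d=0.3, n=80: Φ(2.587 − 2.683) = 46%; n=108: 30%.

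Omnibus test, with largest difference 0.2 SD and noncentrality n×SS(means)/0.5:

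| Four product means | Non-significant, n=80 | n=108 |
|---|---|---|
| 0, 0, 0.2, 0.2 | 46% | 31% |
| 0, 0.2, 0.2, 0.2 | 58% | 45% |
| 0, 0.1, 0.1, 0.2 | 71% | 62% |

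**H1a, what a similarity test could deliver.** For one outcome, with an illustrative margin of 0.33 SD, 90% intervals and three contrasts sharing UBMC (simulated):

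| True differences | One alternative, n=80 / 108 | All three, n=80 / 108 |
|---|---|---|
| 0 | 81% / 92.5% | 58% / 82% |
| 0.1 SD, same direction | 64% / 77% | 38% / 56% |
| 0.1 SD, one opposite | 64% / 77% | about 25% / 44% |

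If claims are made product by product with unadjusted 90% intervals, and all three true differences sit at the margin, at least one false similarity claim occurs about 12% of the time (same direction) to 14% (mixed).

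**Number of H1a results.** Six topography measures + (two craving factors + one withdrawal scale)×5 times = 21 per alternative if none is named primary.

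**The case against.** **H1b is only a label.** E.2 compares each product with UBMC on abuse liability, which is H1b's contrast, and E.1 powers H1b's outcomes. This stands. A reader might infer that H1b cannot be tested; the document does not support that.

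**The chi-square is under-specified rather than wrong.** E.2 does not say three categories, 2 df or goodness of fit for H2a, although it does use the last term for H2c. This stands as a caution: the three-category test is the likeliest reading, not a stated fact. No reading is written down that tests nmC against each rival.

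**The examples are chosen to be stark.** With two leaders tied, nmC comes out on top about half the time by symmetry, so the 48% largely restates the assumption. With a clear lead such as 60/25/15, the two approaches nearly always agree. This is fair as to frequency. It does not change what a significant chi-square can establish.

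**The plan never says that non-significance will be read as similarity.** Correct, and a reader should not infer that it does. But E.2 offers H1a no other route to its similarity claim.

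**Part of H1a is testable.** That the alternatives reduce craving and withdrawal is a difference claim, and the pre- and post-smoking measures can address it if time is modelled. Only the similarity part lacks a test.

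**Conclusion.** The concern holds for the similarity part of H1a and for H2a. The logical gap depends on no assumed figure: a difference test without a margin cannot show similarity, and an omnibus test of shares cannot show that nmC leads its nearest rival.

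The sizes do rest on assumptions. They are compound symmetry and differences in SDs of the paired difference for H1a, and invented choice shares and counts for H2a, on the three-category reading. On those terms, at n=80 the planned contrast misses a 0.2 SD difference 79% of the time and 0.3 SD 46%. A chi-square p of 0.00005 can sit beside p=0.91 for nmC against mFLC.

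Confidence is high for H1a and somewhat lower for H2a, because the form of its chi-square is not stated. The H1b point is a minor labelling correction. The data to be collected remain usable, but the wording should be settled before analysis so that margins and contrasts are not chosen after the results are seen.

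**What to change.** 1. **H2a.** State that 'all other alternatives' means each one. Make the primary analysis nmC against mFLC and nmC against mRYO: exact binomial among those choosing either product, two-sided 0.05, both must favour nmC, no alpha split. Keep the chi-square as descriptive. If all others combined is meant, test nmC's share against 50% (this needs 50 of 80, or 65 of 108). Cost: about one sentence, and lower power for a stronger claim, 46% at 50/30/20 and 92% at 60/25/15 with n=80.

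2. **H1a.** Report each alternative-minus-UBMC difference with its confidence interval from the planned model, whatever the omnibus result, and do not conclude similarity from non-significance. Put time in the model for the pre/post reduction part. Then choose one of two courses.
   - Word the similarity part as estimation, which needs no margin and costs no power.
   - Pre-specify primary outcomes, time points and substantively justified margins, and state which outcomes must pass. State also whether all three alternatives must pass (90% intervals, no split) or claims are product by product (adjust across the three, for example alpha 0.05/3). At n=80 and no true difference, 80% power for one comparison needs a margin of about (1.645+1.282)/√80 = 0.33 SD at alpha 0.05, or about 0.38 SD at 0.05/3. Any all-three power quoted at a true 0.1 SD difference must give the assumed directions. Power falls further if several outcomes must all pass.

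3. **Labels.** Mark the satisfaction and purchase-task power in E.1 as H1b, and add H1b to the E.2 heading for the difference tests.

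No extra data are needed; the changes are to the wording of E.1 and E.2.
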